9.7 Prohibited Concomitant Therapies

Subjects should be instructed not to take any medications, including over-the-counter products, without first discussing with the Investigator.

Supplemental TM buprenorphine (after SUBLOCADE injection) may only be permitted after discussions with the medical monitor.

Due to additive pharmacologic effects, the concomitant use of benzodiazepines or other CNS depressants, including alcohol, increases the risk of respiratory depression, profound sedation, coma and death.

The SUBLOCADE USPI should be referenced regarding use of the below concomitant therapies.

- benzodiazepines and other CNS depressants
- cytochrome P450 3A4 inhibitors or inducers (see [Appendix 1](#))
- antiretrovirals: non-nucleoside reverse transcriptase inhibitors (NNRTIs)
- antiretrovirals: protease inhibitors
- serotonergic drugs
- monoamine oxidase inhibitors (MAOIs)
- muscle relaxants
- diuretics
- anticholinergic drugs

The Indivior medical monitor should be notified if a subject receives any of these treatments during the study.

9.8 Lifestyle Restrictions

Eligible subjects will be advised to abstain from short-acting opioids (such as morphine sulfate, oxycodone, hydromorphone, oxymorphone or codeine) for at least 6 hours and long-acting opioids (such as methadone or levorphanol) for 24 hours before arriving at the clinic on the morning of Day 1. Eligible subjects will be informed that under-reporting of the last use of opioids puts him/her at higher risk for rapid and intense onset of withdrawal symptoms.

Eligible subjects will be advised to abstain from alcohol before checking into the clinic for Day 1 procedures and throughout the study, as central nervous system depressants increase the risk of respiratory depression, profound sedation, coma and death in patients taking buprenorphine ([SUBLOCADE USPI](#)).

9.9 Permitted Concomitant Therapies

The Investigator may prescribe concomitant medications or treatments deemed necessary to the subject, except those medications defined in Section [9.7](#) of this protocol.

Subjects experiencing precipitated withdrawal will be treated for withdrawal symptoms. If precipitated withdrawal occurs before SUBLOCADE administration, the TM induction may be restarted later on the same day at the discretion of the Investigator, based on the half-life of the opioid reported on the TLFB. Alternatively, the Investigator may permit

the subject to return to the facility on another day (within the Screening Period). Returning subjects will repeat all Day 1 scheduled assessments.

If the subject experiences withdrawal symptoms at any time (including precipitated withdrawal after SUBLOCADE), he/she may be treated symptomatically ([SAMHSA TIP 63 2018](#)):

- Nausea: ondansetron or metoclopramide
- Diarrhoea: loperamide
- Anxiety, irritability, sweating: clonidine
- Insomnia: diphenhydramine, trazodone
- Pain: nonsteroidal anti-inflammatory drugs

Supplemental TM buprenorphine (after SUBLOCADE administration) may only be permitted after discussions with the medical monitor. Subjects will not be discontinued from treatment due to illicit opioid use (including buprenorphine).

9.10 Compliance

All study drugs will be administered in the clinic and documented in the source and recorded in the eCRF.

SUBLOCADE compliance will be assessed by inspecting the injection site for evidence of attempted removal of the depot by the subject, documented in the source and recorded in the eCRF. Likewise, surgical removal by a physician will be documented in the source and recorded in the eCRF. See Section [10.7](#) for details on reporting depot removal.

Use of prohibited concomitant medications will be evaluated per the Concomitant Medication assessment outlined in the [Table 1](#) and [Table 2](#), documented in the source and recorded in the eCRF.

9.11 Reporting Product Complaints

The Investigator and study clinic staff are responsible for prompt recognition and reporting of product quality complaints to Indivior. A product complaint is any concern pertaining to the manufacturing or quality control of the study drug and includes, but is not limited to, e.g., short counts/empty pouches, leaking syringes, broken needles, labelling defects, missing inserts, packaging defects or difficult to open packaging, study drug that is thought to be ineffective, or has an appearance, taste or odour that is outside of what is expected.

All product complaints should be reported to Indivior in a timely manner and the following information provided:

- study number
 - site contact/reported by
 - subject number (if already assigned to a subject)
-

- description of issue
- picture, if available (photographs should be taken only if safe to do so/within site policy or practice to take photograph)

If the product has not yet been opened (i.e., product does not pose any hazard), retain the product and packaging in a quarantined space until further instruction is provided by Indivior. If the product is potentially hazardous, dispose per site process and document in the source.

10 ADVERSE EVENTS

The Investigator or designee is responsible for identifying, documenting and reporting events that meet the definition of an AE.

An AE is any untoward medical occurrence in a subject associated with the use of a study drug regardless of the presence of a causal relationship to the study drug. An AE can be any unfavourable and unintended sign (including an abnormal laboratory finding) symptom or disease (new or exacerbated) temporally associated with a study drug, whether or not considered related to the study drug.

Events meeting the definition of an AE include:

- New condition detected after study drug administration even though the AE may have been present prior to receiving study drug.
- Exacerbation of a pre-existing condition (including intensification of a condition and/or an increase in frequency).
- Any abnormal laboratory test results or other safety assessments felt to be clinically significant in the opinion of the Investigator (including those that worsen from baseline).
- Symptoms and/or the clinical sequelae of a suspected interaction or an overdose of either study drug or a concomitant medication
- Signs, symptoms or the clinical sequelae resulting from special interest conditions (e.g., medication error, SUBLOCADE depot removal, etc.).
- Symptoms and/or clinical sequelae resulting from lack of efficacy will be reported if they fulfil the definition of an AE.
- Symptoms and/or clinical sequelae that resulted in intervention.
- Evidence of a subject attempting removal of the SUBLOCADE depot

Events that do not meet the definition of an AE include:

- Medical or surgical procedures; the condition that leads to the procedure is an AE.
 - Situations where an untoward medical occurrence did not occur (e.g., social and/or convenience admission to a hospital, hospitalisation for elective surgery, hospitalisation for observation in the absence of an AE).
 - Anticipated day-to-day fluctuations of pre-existing disease(s) or condition(s) present or detected at the start of the study that do not worsen.
-

10.1 AEs of Special Interest

In this study, AEs of special interest include the following:

- SUBLOCADE depot removal (see Section 10.7)
- Occurrences of ALT $\geq 3 \times$ ULN and bilirubin $\geq 2 \times$ ULN (> 35% direct) are defined as SAEs of special interest

These AEs of special interest should be reported to Indivior, by the Investigator (or designee) **within 24 hours** from first being aware of the event, using the same reporting process as for SAEs, see Section 11.2.

10.2 Assessing and Documenting Adverse Events

The Investigator is ultimately responsible for assessing and reporting all AEs as outlined in the protocol. The assessment and reporting of AEs may be delegated to a medically qualified sub-Investigator, trained on this study protocol, who is listed on the delegation of authority log. All AEs regardless of suspected causal relationship to the study drug will be reported as described in this protocol.

Adverse events should be volunteered by the subject or solicited from the subject using a standard statement, obtained from examination of the subject at a clinic visit, or from observations of clinically significant laboratory values or special examination abnormal values. If an event assessed by one of the study scales requires intervention, or if in the opinion of the Investigator, it is clinically significant, then it will be reported as an AE.

All AEs are to be assessed and recorded in a timely manner and followed to resolution or until the Investigator determines that there is not an anticipated resolution. Each AE is to be documented with reference to severity, date of occurrence, duration, treatment and outcome. Furthermore, each AE is to be classified as being serious or non-serious. In addition, the Investigator must assess whether the AE is study drug-related or not.

10.3 Time Period for Collecting Adverse Events

Adverse events will be collected from the time of signed informed consent until completion of the EOT visit. Any subject with ongoing AEs at the EOT and not continuing MOUD will also be followed up by phone 2 weeks later for the EOS visit (Day 43) to assess the ongoing AEs.

Subjects with ongoing SAEs at the EOS telephone contact that, in the opinion of the Investigator, are associated with the study drug, will be followed and reported as described in Section 11. Subjects with ongoing AEs at EOS telephone contact that, in the opinion of the Investigator, are associated with the study drug, will be followed and reported as described in Section 10.2.

10.4 Assessment of Intensity

The term “severe” is used to describe the intensity (severity) of a specific event (as in mild, moderate, or severe); the event itself, however, may be of relatively minor medical significance (such as a severe headache). This is not the same as “serious”, which is based on subject/event outcome or action criteria usually associated with events that pose a threat to a subject’s life or functioning. Seriousness (not severity) serves as a guide for defining regulatory reporting obligations.

| Intensity | Definition |
|-----------|---|
| Mild | Causes transient or mild discomfort; no limitation of usual activities; no medical intervention required |
| Moderate | Causes mild to moderate limitation in activity; some limitation of usual activities; no or minimal medical intervention or therapy is required |
| Severe | Causes marked limitation in activity; some assistance is usually required; medical intervention or therapy is required; hospitalisation is probable |

Adverse events with changes in severity should be documented as separate events.

10.5 Assessment of Causality

The Investigator or a medically qualified sub-Investigator, trained on this study protocol, listed on the delegation of authority log is responsible for determining the AE relationship to the study drug.

The following categories will be used to define the relationship of an AE to the administration of the study drug:

Not Related: Data are available to identify a clear alternative cause for the AE other than the study drug.

Related: The cause of the AE is related to the study drug and cannot be reasonably explained by other factors (e.g., the subject’s clinical state, concomitant therapy and/or other interventions).

A “reasonable possibility” is meant to convey that there are facts/evidence or arguments to suggest a causal relationship, rather than that a relationship cannot be ruled out. The Investigator will use clinical judgment to determine the relationship. Alternative causes, such as natural history of the underlying diseases, concomitant therapy, other risk factors and the temporal relationship of the event to the study drug will be considered and investigated. The Investigator will also consult the USPI in the determination of his/her assessment. For each AE/SAE, the Investigator must document in the medical notes that he/she has reviewed the AE/SAE and has provided an assessment of causality.

There may be situations when an SAE or AE of special interest has occurred, and the Investigator has minimal information to include in the initial report to Indivior or designated representative. However, it is imperative that the Investigator always make an assessment of causality for every event prior to the initial transmission of the SAE or AE of special interest data to Indivior or designated representative. The Investigator may change his/her opinion of causality in light of follow-up information and amend the SAE or AE of special interest data collection tool accordingly. The causality assessment is one of the criteria used when determining regulatory reporting requirements.

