3.3 Other Safety Assessments

Major safety endpoints will include the proportion of subjects with TEAEs of the following types at any time during the treatment period (i.e., any time after administration of TM buprenorphine): TEAE, drug-related TEAE, serious TEAE, drug-related serious TEAE and TEAE leading to treatment discontinuation.

Additional safety endpoints will include assessment of laboratory results, vital signs and concomitant medications.

Withdrawal symptoms will be monitored by COWS (secondary endpoint), AEs, opioid craving (using OC-VAS; secondary endpoint) and sedation (using Sedation VAS).

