9 STUDY DRUG MANAGEMENT

The term "study drug" is used throughout the protocol to describe the TM buprenorphine and/or SUBLOCADE received by the subject as per the protocol design. Study drug may therefore refer to TM buprenorphine and/or SUBLOCADE.

The clinic will source commercially available TM buprenorphine for the study; SUBLOCADE will be provided by the Sponsor.

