11.2.2 Regulatory Reporting Requirements for Serious Adverse Events

Prompt receipt of notifications of SAEs to Indivior or designated representative from Investigators is essential in ensuring that legal obligations and ethical responsibilities regarding the safety of subjects are met.

Indivior has a legal responsibility to notify both the local regulatory authority and other regulatory agencies about the safety of a study drug. Indivior or designated representative will comply with country-specific regulatory requirements pertaining to safety reporting to Regulatory Authorities, IRBs and Investigators.

A suspected unexpected serious adverse reaction (SUSAR) is an SAE related to the study drug administered in any dose and that, in its nature or severity, is inconsistent USPI. Indivior Global Safety will determine if an SAE meets the definition of a SUSAR and distribute SUSAR reports according to local regulatory requirements and Indivior policy. An Investigator who receives the safety report describing an SAE or other specific safety information (e.g., summary or line listing of SAEs, Dear Investigator Letter) will file it with the USPI and will notify the IRB, if required according to local requirements.

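### The two causality categories in Protocol 10.5 leave a gap, and for withdrawal-type adverse events that gap can lean ratings away from Related

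*Protocol*

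**What the plan says.** Protocol 10.5 offers two categories and no third (such as possible or unknown).

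- An event may be called Related on this condition: "The cause of the AE is related to the study drug and cannot be reasonably explained by other factors". The bracketed examples begin with the subject's clinical state, then concomitant therapy and other interventions.
- An event may be called Not Related on a different condition: "Data are available to identify a clear alternative cause for the AE other than the study drug".

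The next paragraph explains reasonable possibility. There must be something positive that points to a causal link, "rather than that a relationship cannot be ruled out". Neither category uses the term. The section then adds: "The Investigator will use clinical judgment to determine the relationship". Alternative causes, timing and the USPI are to be weighed.

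Protocol 10.2 asks for one answer per event: "In addition, the Investigator must assess whether the AE is study drug-related or not". Protocol 9 says what that answer refers to: "Study drug may therefore refer to TM buprenorphine and/or SUBLOCADE".

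The rating is then used in several places. Protocol 3.3 lists "drug-related TEAE, serious TEAE, drug-related serious TEAE and TEAE leading to treatment discontinuation" among the major safety endpoints, and Protocol 14.5.1 and SAP 5.5.2 tabulate them. Under Protocol 11.2.2 a SUSAR "is an SAE related to the study drug administered in any dose" and is also inconsistent with the USPI. Under Protocol 10.3, follow-up of events still ongoing at the end-of-study call depends on association with study drug.

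**The concern.** A two-level rating should partition the events, so that each event meets exactly one definition. Here the middle ground is undefined, and in this trial the middle ground is where the main risk lies. Protocol 1.3.1 names precipitated withdrawal, possibly prolonged after the injection, as the risk of early dosing. The same subjects must already be in withdrawal to be dosed, so their clinical state, the first listed reason for not choosing Related, is a ready explanation for a withdrawal-type event.

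The design gives no protection against such a lean. There is one arm, so no comparator carries the same misclassification, and the drug-related percentage will be read at face value. With about 15 subjects, one subject moved out of the related count shifts the percentage by 1/15 = 6.7 points.

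**Working it through.** **Step 1. Do the two definitions cover every event?**

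| Evidence for a non-drug cause | Meets Related? | Meets Not Related? |
|---|---|---|
| No reasonable alternative | Yes, if the drug is judged the cause | No |
| Plausible alternative, not clear | No | No |
| Clear alternative, supported by data | No | Yes |

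The definitions do not overlap, but the middle row has no home. Section 10.5 still requires a causality assessment for every event before an SAE or AE of special interest is first transmitted, so the investigator must pick one.

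**Step 2. Which events fall in the middle row?** Protocol 5.6 requires COWS of at least 8 before transmucosal buprenorphine. Sections 4.1 and 9.9 allow symptomatic medication for withdrawal at any time and keep subjects in treatment despite illicit opioid use. Clinical state, concomitant therapy and continued use are therefore often available as explanations. Only new or worsened events count as TEAEs (Protocol 14.5.1, SAP 5.5.2), so the events at issue are withdrawal-type events that began or intensified after buprenorphine. For these, underlying withdrawal is plausible but usually not clear.

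**Step 3. What depends on the rating?**

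- Dependent: drug-related TEAEs, drug-related serious TEAEs, the investigator's causality input to SUSAR assessment, and follow-up beyond the end-of-study call.
- Not dependent: all-cause and serious TEAE counts, the COWS rise of at least 6 (SAP 5.3.1 and 5.3.2), COWS AUC, and adjudicated withdrawal (SAP 5.3.3.2).

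**Step 4. How large could the effect be?** The documents give no figure for it. For scale only, Protocol Table 4 reproduces at n = 15: 1 − 0.90^15 = 0.794 and 1 − 0.95^15 = 0.537. That table concerns precipitated withdrawal, not relatedness.

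Now assume that p is the true proportion of subjects with a drug-caused withdrawal AE, and f is the share of those subjects whose event is rated Not Related. The chance that at least one of 15 subjects is counted as related is 1 − (1 − p(1 − f))^15.

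| f (assumed) | p = 10% (assumed) | p = 20% (assumed) |
|---|---|---|
| 0 | 0.794 | 0.965 |
| 25% | 0.689 | 0.913 |
| 50% | 0.537 | 0.794 |
| 75% | 0.316 | 0.537 |
| 100% | 0 | 0 |

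Misrating half of such events has the same effect as halving the true rate. Nothing in the documents fixes f, so the table gives a range and not an estimate.

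**The case against.** The best reply is that the wording does not decide these events. A withdrawal event with only a plausible alternative fails Not Related as well, so it passes to clinical judgement. Timing can favour Related, and so can Protocol 1.3.1, which lists drug withdrawal syndrome as a commonly reported AE of buprenorphine. Several filters also help. Fluctuations that do not worsen are not AEs (Protocol 10), and the injection is withheld if precipitated withdrawal followed the latest transmucosal dose (Protocol 5.7). SAP 5.5.2 counts a subject at the most related occurrence of a preferred term. On reporting, SAEs reach the sponsor within 24 hours, and the sponsor's safety group decides SUSAR status.

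Most of this stands, and it limits the claim to a risk of bias. It does not close the gap. Judgement has to be exercised through definitions, and the only one that mentions clinical state uses it against Related. The most-related rule helps only if some occurrence was rated Related. The COWS and adjudication analyses do not use the rating, so they can neither be biased by it nor correct it. Post-injection adjudication also stops at 48 hours, while TEAEs are collected to the end of treatment.

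A reader might also infer that, with one rating for two products, events cannot be tied to SUBLOCADE at all. The documents do not support that. SAP 5.5.2 shows related TEAEs separately by onset in induction and after the injection, repeats the AE summaries for onset within 48 hours of the injection, and lists COWS values, AEs and dosing times chronologically. The adjudication committee judges the two periods separately. What remains is that the rating itself does not separate the products after the injection, where onset time is only a proxy. Both products deliver buprenorphine about 1 hour apart and the objective concerns the sequence, so a per-product rating of systemic events would have limited value.

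**Conclusion.** The point holds as a wording defect with a foreseeable direction. The two categories are not exhaustive, the standard that 10.5 explains is attached to neither, and for withdrawal-type events the text leans away from Related. The drug-related and drug-related serious TEAE counts can be biased downward, and causality-based reporting can be affected.

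It would go too far to say that withdrawal events will be removed from the related counts, or that the related percentage would fall to zero. That needs every such event to be rated Not Related, and the text does not direct this.

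The conclusion assumes that investigators apply 10.5 roughly as written and that the AE form adds no further guidance. The form is not among the documents, so the second assumption, and whether a per-product rating is already collected, cannot be checked.

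**What to change.** In Protocol 10.5, replace the two definitions:

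- *Related: there is a reasonable possibility that the study drug caused the event.*
- *Not Related: there is no reasonable possibility that the study drug caused the event.*

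Keep the existing explanation of reasonable possibility, so that Related still needs positive grounds. Each event then falls in exactly one category. Alternative causes, including underlying withdrawal, remain part of the judgement but no longer rule out Related merely by being plausible.

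SAP 5.6 refers to re-training on 08 October 2019, so subjects may already have been rated. Those ratings should be reviewed under the new wording, or the study report should state which definition applied.

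The cost is a short amendment and a site briefing. The drug-related percentage may look less favourable. Recording causality separately for transmucosal buprenorphine and SUBLOCADE is optional, because the SAP's tables by onset phase already go part of the way.

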10.6 Clinical Laboratory Changes

Changes in laboratory values or other safety parameters (e.g., neurological and clinical symptom assessments) as noted in the protocol are a sub-set of AEs and are reportable only if the lab test result is associated with accompanying symptoms, and/ or requires additional diagnostic testing or intervention (medical, surgical), and/or requires additional significant treatment, and/or requires temporal or permanent discontinuation of study drug, or a change to dosing other than as permitted by protocol, or if considered to be clinically significant by Investigator or medically qualified designee.

Screening laboratory assessments, if determined to be clinically significant by the Investigator, are not AEs.

Guidance for the procedures to follow for elevated liver function tests are provided in Section [8.2.7.3](#).

